## 4.12 ECGs analyses (adjudicated)

Analysis of drug related QT/QTc interval changes relative to plasma PK concentrations is optional and will be conducted as required. This analysis will focus on the known PGP-induced QTc prolongation and possible impact of PYR on this effect. The principles of this analysis follow the statistical methods described by Garnett et al., 2018 [1]. This analysis will be performed on the analysis set for intensive cardiac assessment.

In addition, a per timepoint analysis will be performed. While this analysis is based on minimal assumptions on the nature of the data, it has limited power to show the absence of a prolonging effect. On the other hand, the concentration-QTc analysis has been shown to have this power, but it is based on more restrictive assumptions. Concentration/ QTc modelling may be performed after completion of the Clinical Study Report and will be delivered in a separate report.

### Baseline

For all quantitative parameters, baseline will be the average over the values obtained at the three pre-dose timepoints of Day 1.

### Heart rate correction

QTcF will be used for ECG analyses unless there is an effect of one of the drugs on HR exceeding 10 bpm. Evidence of the absence of such an effect will be considered given, if either the absolute mean time matched difference to placebo is below 10 bpm for all timepoints and for both monotherapies and the combination therapy or a concentration-effect model similar to the one described for QTc below excludes an effect exceeding 10 bpm at relevant concentrations. If an effect of the therapy on HR cannot be excluded following the criteria above, QTcI and QTcS will be determined based on data extracted from the 24h Holter data and the primary correction method will be selected based on the mean squared slope criteria. More specifically, around 30 ECG snapshots will be extracted from Holters spread across the whole recording of Day 1, aiming to capture wide variety of HR values and RR and QT values determined. For each subject, these RR/QT pairs will be ranked by heart rate and the pairs with odd rank assigned to the training set and the remaining ones to the validation set. Based on the data in the training set, a regression of the form

$$\log(QT) \sim \log(RR) + 1$$

will be performed. Let  $\beta_i$  be the regression coefficient ("slope") thus obtained for subject  $i$ , then the individual correction for this subject will be

$$QTcI_i = \frac{QT}{RR^{\beta_i}}$$

The exponent for the study-specific correction (QTcS) will be the median of the individual  $\beta_i$  across subjects and the correction will be calculated along the same lines.

For each subject  $i$  and each of the three correction methods QTcF, QTcI and QTcS, a linear regression on the pairs of RR and QTc in the validation set of that subject will be fitted and the slope  $b_{ik}$  for the regression of the validation data of subject  $i$  with method  $k$  be obtained. For each method, the mean squared slope across

subjects will be determined and the method with the smallest mean slope will be used as primary correction method.

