Cardiovascular system	
PQP: alone known to induce QTc prolongation in human participants with a well-documented exacerbation when the drug is taken with food [12,13]; also associated with tachycardia.
 
Please see Risk Management text above for further details.
	
 
1) Comprehensive monitoring and intensive cardiac assessments (including screening Holter and Telemetry D1-D3 with intensive time matched 12-Lead ECGs on D1 and D3).
 
2) Three hour fasted state dosing to reduce Cmax of PQP and QTcF risk. Four hour post dose fast also.
 
3) Exclusion of participants on QTcF prolonging medications (Section 5.4)
 
4) Strict Exclusion Criteria surrounding history of
 

	
PYR: not known to induce clinically concerning QTc prolongation in human participants but no formal concentration/QTc modelling in healthy participants is available.
	

Target System	Effect	Risk Mitigation
	
Phase I CYP3A4 DDI study of Pyronaridine-DHA with ritonavir, there was no relationship between QTcF change and plasma concentrations of pyronaridine or DHA [23].
 
PYR: more commonly associated with bradycardia in patients. Decrease in heart rate correspond to reduction in fever of malarial infection.
 
PYR use associated with palpitations and ventricular extrasystoles albeit uncommon (<math>\geq 1/1000</math> to <math>< 1/100</math>).
	predisposing cardiac conditions (Section 5.4).
Respiratory System	
PQP: No effects noted in human studies.
 
PYR:  Pre-Clinical Study:  A transient increase in respiratory rate was observed at a dose of 500 mg/kg two hours post- dose in a pre-clinical study in guinea pigs. No effects noted at doses of 33 and 100 mg/kg or at any other timepoint [19].
 
Human Malarial Studies:  Bronchitis, rhinitis and cough have uncommonly been seen in PYR-AS combination treatment of uncomplicated malaria.
	1) Standard monitoring as with all early phase studies.
Central nervous system	
POP: headache (common), dizziness (uncommon) and convulsion (rare/very rare) has been seen in DHA-PQP combination clinical trials.
 
Asthenia commonly seen in DHA-PQP combination.
	1) Standard monitoring as with all early phase studies. 2) Warning regarding driving or operating machinery upon discharge if dizziness or fatigue/asthenia occurs.

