**Table 5: Schedule of Assessments**

Procedure	Screening (D-22 to D-2)	D-1	D1	D2	D3	D4	D5	D6	D7  Sentinel Group only	D8	D15	D22	Last visit D30 (±1)	
In-house stay		X	X	X	X	X	X 	X	X					
Outpatient visit								X		X	X	X	X	
Informed consent	X													
Eligibility check	X	X												
Medical history/ demographics	X	X 												
Prior & concomitant medications	X	X	X	X	X	X	X	X	X	X	X	X	X	
Smoking history and current	X													
Beck depression inventory questionnaire	X													
Urine drugs of abuse screen	X	X												
Alcohol breath test	X	X												
Serology HIV 1&2, Hepatitis B&C	X													
Serum pregnancy test (females)	X	X											X	
FSH (post- menopausal females)	X													
Randomisation			X											
Trial drug administration 			X	X	X									
Meals 		X	X	X	X	X	X	X	X	X				
Safety and tolerability:														
Vital signs 	X	X	X	X	X	X	X	X	X	X	X	X	X	
12-lead ECG 	X	X	X	X	X	X	X	X	X	X	X	X	X	
24-hour Holter ECG	X													
Telemetry 			X	X	X									
BMI calculation	X	X 												
Physical examination 	X	X	X	X	X	X	X	X	X	X			X	

Procedure	Screening (D-22 to D-2)	D-1	D1	D2	D3	D4	D5	D6	D7  Sentinel Group only	D8	D15	D22	Last visit D30 (±1)	
Biochemistry, Haematology, Coagulation 	X	X	X	X 	X 	X	X	X	X	X	X	X	X	
Urinalysis	X	X	X		X		X		X	X	X	X	X	
Pharmacokinetics:														
PK sampling – PYR 			X	X	X	X		X		X	X	X		
PK sampling – PQP  (including e.g. N- oxidated metabolite)			X	X	X	X		X		X	X	X		
Pharmacogenomics:														
CYP polymorphism				X										

1. Vital signs (supine blood pressure, heart rate and respiratory rate) will be measured after rest of at least five minutes in supine position. Tympanic body temperature will be taken at each time-point (resting in supine position is not required for body temperature). Standing blood pressure and heart rate will be performed one minute after standing to assess for orthostatic change at screening and on Day -1, Day 1 and Day 3. See Table 6 for Time-points.
2. 12-lead ECG will be measured in triplicate after a rest period of at least ten minutes in supine position. See Table 6 for time-points.
3. Full physical examination at screening and last visit only. Symptom-directed physical examinations at other time-points.

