### **7.9.3 24-hour Holter ECG**

Holter recording will be performed at screening as described in Table 5. Each electronic Holter ECG file will be downloaded onto the GE Gatedmed Holter Analysis system.

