### 10.4.2 Heart rate correction

QTcF will be used for ECG analyses unless there is an effect of one of the drugs on HR exceeding 10 bpm. Evidence of the absence of such an effect will be considered given, if either the absolute mean time matched difference to placebo is below 10 bpm for all timepoints and for both monotherapies and the combination therapy or a concentration-effect model similar to the one described below excludes an effect exceeding 10 bpm at relevant concentrations. If an effect of the therapy on HR cannot be excluded following the criteria above, QTcI will be determined based on data extracted from the 24h Holter data and the primary correction method will be selected based on the mean squared slope criteria [28] using the Day -1 12-lead ECG data. Details will be given in the SAP.

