### 2.2 Endpoints

#### Primary

- The incidence, severity and relationship of Treatment-Emergent Adverse Events (TEAEs).
- Proportion of participants with clinically significant changes in laboratory safety tests (haematology, biochemistry, coagulation and urinalysis).

- Proportion of participants with morphological and/or rhythm abnormalities on electrocardiogram (ECG).
- Proportion of participants with clinically significant changes in ECG time intervals (PR, QRS, QT and QTc intervals) and clinically significant changes against baseline Holter.
- Proportion of participants with clinically significant changes in vital signs (systolic blood pressure, diastolic blood pressure and pulse rate).

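### The fallback heart-rate correction (QTcI/QTcS) is built on a Day 1 Holter that is not scheduled; the only 24-hour Holter is at screening, and the protocol selects the method on Day -1 ECGs

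*SAP*

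**What the plan says.** SAP 4.12 (Heart rate correction) uses QTcF by default. If neither of its two criteria excludes a heart-rate effect above 10 bpm, QTcI and QTcS "will be determined based on data extracted from the 24h Holter data". The next step is specific: "around 30 ECG snapshots will be extracted from Holters spread across the whole recording of Day 1". Each participant's RR/QT pairs are ranked by heart rate. Odd ranks train the exponent, and the remaining pairs decide between QTcF, QTcI and QTcS.

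The protocol describes different recordings. Section 7.9.3 states: "Holter recording will be performed at screening as described in Table 5". The "24-hour Holter ECG" row of Table 5 has a single mark, in the screening column. Table 3 separates the two kinds of monitoring: "including screening Holter and Telemetry D1-D3 with intensive time matched 12-Lead ECGs on D1 and D3". SAP 4.11.4 likewise names telemetry and Holter as two kinds of data.

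Protocol 10.4.2 also takes QTcI from the 24-hour Holter, without naming a day. It then says that "the primary correction method will be selected based on the mean squared slope criteria [28] using the Day -1 12-lead ECG data", and leaves details to the SAP.

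**The concern.** Dosing takes place on the mornings of Days 1, 2 and 3. A heart-rate correction should describe how a participant's QT follows RR without drug, and both recordings that the protocol points to (the screening Holter and the Day -1 ECGs) are pre-dose. The SAP moves the derivation and the selection to a dosing day, gives no reason, and names a recording that is not in the schedule.

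If the analyst substitutes Day 1 telemetry, any drug effect on QT and heart rate enters the fitted slope. The branch opens only when a heart-rate effect is in doubt, which is the condition under which this leakage can arise. Protocol Table 3 says PQP is "also associated with tachycardia", without a size in bpm.

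The analyses at stake are the adjudicated QTc analyses: the per-timepoint difference from placebo, which is a secondary endpoint, and the optional concentration-QTc model. The adverse reaction rules use uncorrected QT, and the un-adjudicated tables use QTcF, so neither is affected.

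**Working it through.** The plan gives no figure for this step, so there is none to reproduce.

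**1. The texts side by side**

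| Item | Protocol | SAP 4.12 |
|---|---|---|
| 24-hour Holter | Screening only (Table 5, 7.9.3, Table 3) | Holters of Day 1 |
| Day 1 continuous recording | 12-lead telemetry from at least 1 h pre-dose (Table 5, footnote 6) | Not named |
| Data for selecting the method | Day -1 12-lead ECGs (10.4.2) | Held-out half of the Day 1 snapshots |

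**2. How much of a Day 1 recording is drug-free.** Assume 1 h pre-dose plus 24 h post-dose and evenly spread snapshots. Then 30 × 1/25 = 1.2 of 30 snapshots are pre-dose. In the planned allocation, 32 of 40 participants (80%) receive an active drug.

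**3. Mechanism.** QTcI = QT / RR^β. If QT lengthens while heart rate rises, the slope of log QT on log RR flattens and the fitted β is too small. A single setting shows this. Assume a true β of 1/3, heart rate 62 bpm (SD 8), a QTc of 405 ms with noise SD 6 ms, and effects peaking at 5 h with a 12 bpm rise and a true effect of 20 ms, all present on Day 1. The fitted β is 0.284, an error of 0.333 − 0.284 = 0.049.

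- At 62 bpm: 405 × (60/62)^0.049 ≈ 404.4 ms
- At 74 bpm: 425 × (60/74)^0.049 ≈ 420.6 ms
- Apparent effect: about 16.3 ms, against a true 20 ms

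A 12 bpm fall also understates the effect (β 0.381, apparent 15.7 ms). With no heart-rate change the result is 20.0 ms. This setting is narrow and is not an estimate for the trial.

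**4. Range of sizes.** The SAP algorithm was simulated with the planned 16/8/8/8 participants and 200 trials per scenario. Thirty evenly spaced snapshots ran from -1 to 23 h on Day 1. The result is the Day 3 peak minus Day 1 pre-dose, minus placebo. The true effects, 15 and 20 ms, are the ends of the range the protocol reports for fasted PQP (section 1, Safety and tolerability).

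These inputs are assumptions:
- a heart-rate rise of 10 or 15 bpm at the Day 3 peak
- spontaneous heart-rate SD of 8, 10 or 15 bpm
- exponent mean 1/3, SD 0.04
- QT noise SD 5 ms
- peak at 5 h in the PQP-containing arms, with 10% or 40% of the effect left at 24 h
- no daily rhythm

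| True effect | Share present on Day 1 | QTcI (ms) | QTcS (ms) |
|---|---|---|---|
| 20 ms | half | 18.8-19.8 | 19.4-19.9 |
| 20 ms | three quarters | 17.6-19.7 | 18.6-19.8 |
| 20 ms | full | 16.0-19.4 | 17.7-19.7 |
| 15 ms | half | 14.1-14.9 | 14.4-15.0 |
| 15 ms | full | 12.0-14.5 | 13.2-14.8 |

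A drug-free recording returns the true value within 0.1 ms. Choosing snapshots evenly over the heart-rate range changes little (true 20 ms, SD 8-10: half, QTcI 18.9-19.7; full, 16.1-18.9). Adding an assumed 8 bpm daily rhythm enlarges the half-effect understatement to about 2.2 ms.

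**5. Does validation catch it?** No. The validation pairs come from the same recording. The held-out half still selects QTcI in 76% to 100% of the evenly spaced trials.

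**6. Can the branch open by chance?** The first criterion needs every time-matched mean difference from placebo to be below 10 bpm in all three active arms. Table 6 gives 28 ECG times after the first dose (9 on Day 1, 6 on Day 2, 13 on Day 3). With no true effect and an assumed within-subject correlation of 0.3 to 0.7, this criterion fails as follows:

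| SD of heart-rate change | Failure by chance |
|---|---|
| 5 bpm | under 1% |
| 6 bpm | 2-4% |
| 7 bpm | 9-18% |
| 8 bpm | 22-42% |

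The second criterion, a concentration-effect model, can still close the branch, but the QTc model it resembles is optional in the SAP.

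**The case against.** The strongest reply is that this is an ambiguity with little consequence. A continuous 12-lead recording does exist on Day 1, and protocol Table 7 allows telemetry in the optional ECG analysis. The SAP's preceding sentence mentions only 24-hour Holter data, so Day 1 may be a drafting slip for screening; the bias would then be nil. Protocol 10.4.2 delegates details to the SAP, and a held-out set may suit the purpose better than Day -1, which has one ECG entry in Table 5 and no times in Table 6. The SAP was completed after recruitment stopped at 37, and the documents do not show which recordings were held by then.

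On size, bias needs several things together: the heart-rate trigger, adjudicated analyses that SAP 4.11.6 makes subject to contract, the use of telemetry, and a drug that moves both QT and heart rate. The protocol already states that PQP exceeds 10 ms, so no false all-clear for PQP follows. The simulation gave both PQP-containing arms the same effect, so the bias should largely cancel between combination and PQP alone; that contrast was not computed.

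Most of this stands as a limit on the impact. The SAP's phrase "clinically significant changes against baseline Holter" also gives no date and adds little either way. None of it repairs the text. A slip still has to be corrected, because otherwise the recording is chosen after heart-rate differences between treatments have been examined. The telemetry reading is not stated in SAP 4.12 and would be almost wholly post-dose. Delegating details does not explain replacing a data source that the protocol names.

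**Conclusion.** The point holds. As written, the fallback names an unscheduled recording on a dosing day and departs from protocol 10.4.2 without a reason. It should be corrected, although its reach is narrow.

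Under the telemetry reading, the error is towards understating QTc prolongation. The protocol expects the maximal effect on the last dosing day (section 1, Potential for interaction), so the half-effect rows fit it better: an understatement of up to about 1.2 ms without daily rhythm. If the full effect were present on Day 1, the understatement would reach 4.0 ms for a true 20 ms (20 − 16.0) and 3.0 ms for a true 15 ms (15 − 12.0). These sizes rest on heart-rate inputs that the documents do not supply. The inconsistency between the texts does not depend on them.

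**What to change.** In SAP 4.12:

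- Replace Day 1 with the drug-free 24-hour screening Holter as the source for deriving QTcI and QTcS.
- State that post-dose telemetry is not used for the correction.
- Name one source for selecting the method and use it in both SAP 4.12 and protocol 10.4.2: either the held-out half of the screening Holter or the Day -1 12-lead ECGs. Both are drug-free. Day -1 keeps to the protocol but offers little heart-rate range for within-subject slopes.
- As a wording correction only, let the final selection rule refer to the smallest mean squared slope.

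The cost is SAP wording, plus one matching protocol line if 10.4.2 changes. No procedure is added, because the Holter is scheduled for every participant. Two limits should be acknowledged. Table 7 lets a Holter from screening for another study be carried over for up to three months, so some exponents would rest on an older recording. Exclusion criterion 10 also accepts an equivalent assessment, so the SAP should say how a participant without a usable screening Holter is handled.

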### Per timepoint analysis

For all quantitative ECG parameters, descriptive statistics will be given for the change from baseline. In addition, for QTc, a linear model with the two treatments (PYR and PQP) and their interaction as factors and baseline as covariate will be fitted for each timepoint; the difference between each of the active treatments and placebo will be estimated based on this model; and two-sided 90% confidence intervals (CI) will be given.

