### **7.9.5 Analysing and over-reading 12-lead ECG for the purpose of intensive cardiac assessments**

Each electronic ECG will contain the ECG data as well as the result of the automated ECG analysis performed by the Marquette® 12SL™ ECG Analysis Program, a program resident in each of the ECG machines. All of the ECG and its associated automated interval measurements will subsequently be reviewed by qualified cardiologists in accordance with the ICH E14 Guidance for Industry document and ICH E14 Implementation Working Group Questions and Answers document, before any of the ECG is used for the thorough ECG analysis. The manual adjudication process applied in this trial is also referred to in the ICH guidance and relevant literature as 'manual over-read', 'computer-assisted' or 'semi-automated' ECG measurements. The following parameters on each ECG will be assessed by a cardiologist using the commercially available MUSE® in its latest version. The intention is to also measure sub-intervals:

- QT interval and sub intervals
- RR interval
- heart rate (HR)
- PR interval
- presence or absence of U-wave
- quantitative and qualitative ECG variations.

Manual on-screen over-reading using electronic callipers in MUSE® will be performed by a small and select group of cardiologists with extensive experience

---

with manual QT measurement (including on-screen measurement with electronic callipers). For all trial ECG the over-reading cardiologists will be blinded to time, date, treatment and any data that identify the participant. All ECGs of a given participant will be over-read by the same cardiologist (or cardiologists in case manual adjustments of the automated measurement are necessary).

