#### Secondary

- To determine the pharmacokinetics (PK) of PYR and PQP when administered alone, and in combination, for three days.
- To determine the relationship between PQP and ECG parameters (QTc, QRS and PR), between PYR and ECG parameters, and to evaluate any impact of the combination of PYR and PQP on ECG parameters.

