## Secondary

- PK parameters derived by non-compartmental methods including maximum observed plasma concentration (Cmax), time to reach maximum plasma concentration (tmax), area under the plasma concentration-time curve from time zero to last detectable plasma concentration (AUC0-t), area under the plasma concentration-time curve from time zero extrapolated to infinite (AUC0-∞), apparent total plasma clearance (CL/F), apparent volume of distribution during the terminal phase (Vz/F), terminal elimination rate constant (λz), and terminal elimination half-life (t1/2).

Difference between baseline corrected QTc following placebo and baseline corrected QTc following PQP alone, and with PYR.

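### The secondary ECG objective covers QRS and PR as well as QTc, but the per-timepoint model that gives placebo differences, the PYR x PQP interaction and 90% CIs is planned for QTc only.

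*SAP*

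**What the plan says.** **Objective.** SAP 2.1 and Protocol 2.1.2 set the secondary ECG objective, which also takes in what the two drugs do when given together: "To determine the relationship between PQP and ECG parameters (QT c , QRS and PR), between PYR and ECG parameters". QRS and PR are written out beside PQP only. For PYR and the combination the text says ECG parameters, which reads most naturally as the same list.

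**Endpoint.** The matching secondary endpoint (SAP 2.2, Protocol 2.2.2) is "Difference between baseline corrected QT c following placebo and baseline corrected QT c following PQP alone, and with PYR".

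**Per-timepoint analysis.** SAP 4.12 and Protocol 10.4.3 open with "For all quantitative ECG parameters, descriptive statistics will be given for the change from baseline". They continue: "In addition, for QT c , a linear model with the two treatments (PYR and PQP) and their interaction as factors and baseline as covariate", fitted at each timepoint, from which each active treatment is compared with placebo and "two-sided 90% confidence intervals (CI) will be given".

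**Concentration model.** Its only outcome is the change in QTc, and SAP 4.12 makes it optional.

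**Where else PR and QRS appear.** They are in the primary safety endpoint on clinically significant changes in ECG intervals (SAP 2.2). SAP 4.11.6 gives descriptive summaries, flags against reference ranges (PR 120-220 ms, QRS up to 120 ms), counts of out-of-range and clinically relevant values, and one outlier category each, all on un-adjudicated ECGs. SAP 4.11 plans no formal statistical analysis of safety data.

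**Heart rate.** SAP 4.12, Heart rate correction, keeps QTcF if "the absolute mean time matched difference to placebo is below 10 bpm for all timepoints" for both monotherapies and the combination, or if a concentration-effect model excludes an effect above 10 bpm.

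**The concern.** The objective asks how each drug relates to PR and QRS and what the combination adds. For QTc the 2 x 2 model answers this directly: a difference to placebo for each active arm, an interaction term and an interval. For PR and QRS the reader gets separate arm summaries and has to do the comparison unaided.

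Change from baseline within an arm also carries time of day, meals and enforced semi-supine rest. Protocol 3.4 gives the reason for the placebo arm as telling treatment effects apart from effects of setting and procedure. For PR and QRS no planned estimate puts that arm to use.

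The outlier categories are a coarse substitute. Each needs a rise of more than 25% that also crosses a fixed limit. From an illustrative PR of 160 ms the rise must exceed 40 ms (160 x 1.25 = 200), and from an illustrative QRS of 96 ms it must exceed 24 ms (96 x 1.25 = 120). A smaller shift shared by a whole arm could produce no outlier. Conduction is not a remote subject here: Protocol 8.2.5 lists second- or third-degree AV block and bundle branch block among the adverse events of special interest.

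**Working it through.** **1. Objective against analysis, by parameter**

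| | QTc | PR | QRS |
|---|---|---|---|
| Named in the secondary objective | yes | yes | yes |
| In the secondary ECG endpoint | yes | no | no |
| By-arm descriptives, placebo included | yes | yes | yes |
| Outlier and out-of-range counts | yes | yes | yes |
| Model-based difference to placebo with 90% CI | yes | no | no |
| PYR x PQP interaction estimate | yes | no | no |
| Concentration model (optional) | yes | no | no |

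No section of either document fills the empty cells for PR or QRS.

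**2. The plan's own sample-size figures.** SAP 3.2 gives 81% and 97% for seeing at least one event in 16 participants. These reproduce: 1 - 0.9^16 = 0.815 and 1 - 0.8^16 = 0.972. They concern detecting an event and say nothing about the precision of a PR or QRS difference.

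**3. Precision if the same model were fitted to PR and QRS**

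Inputs: planned arms of 16, 8, 8 and 8 (SAP 3.1); a two-sided 90% CI (SAP 4.12); four treatment cells plus one baseline covariate, so df = 40 - 5 = 35 and t(0.95, 35) = 1.690. The documents give no SD for change in PR or QRS. I assume a residual SD of 8 ms with a range of 6 to 10, and baselines balanced across arms.

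Half-width for two arms = t x SD x sqrt(1/n1 + 1/n2). For the interaction the root is sqrt(1/16 + 1/8 + 1/8 + 1/8).

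| Contrast | Root term | In SD units | SD 6 | SD 8 | SD 10 |
|---|---|---|---|---|---|
| Monotherapy vs placebo (8 vs 8) | 0.500 | 0.845 | 5.1 ms | 6.8 ms | 8.4 ms |
| Combination vs placebo (16 vs 8) | 0.433 | 0.732 | 4.4 ms | 5.9 ms | 7.3 ms |
| PYR x PQP interaction | 0.661 | 1.118 | 6.7 ms | 8.9 ms | 11.2 ms |

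(The 8.4 is 8.448 before rounding; with 34 df it is 8.45, shown elsewhere as 8.5.)

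**4. With 37 recruited.** SAP 3.2 says recruitment stopped at 37 and gives no split by arm. With df = 37 - 5 = 32, if all three missing participants fell in one 8-participant arm, 8 vs 5 gives 0.966 SD (7.7 ms at SD 8). If they fell in the combination arm, 13 vs 8 gives 0.761 SD (6.1 ms).

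**5. Amount of added output.** Protocol Table 6 has 9 post-dose ECG times on Day 1, 3 on Day 2 and 9 on Day 3, which makes 21. Three active-versus-placebo contrasts at each give 21 x 3 = 63 intervals per parameter: 126 for PR and QRS, and 189 if heart rate is added. Later visits would add more.

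**The case against.** The strongest reply is that PR and QRS are far from ignored. They sit in the primary safety endpoint, are flagged and counted, and are summarised by treatment group beside a concurrent randomised placebo arm on the same schedule. From the tabulated n, mean and SD a reader could derive an unadjusted difference and interval. The trial is exploratory with no formal sizing, and Protocol section 1 names gastrointestinal, hepatic and QTc effects as the toxicities of focus, so confining the model to QTc is a defensible priority. All of that stands and limits the weight of the point. It does not supply a baseline-adjusted difference, an interval or an interaction estimate for parameters that the objective itself names.

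Three stronger readings may tempt a reader, and the documents support none of them.

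- **That rate and conduction effects cannot be separated from study procedures.** The placebo arm is summarised at the same timepoints, so they can be compared, though informally. For heart rate, SAP 4.12 already provides a time-matched difference to placebo or a concentration-effect model. Protocol Table 3 also links the bradycardia seen with PYR in patients to falling fever.
- **That QRS is not over-read.** Protocol 7.9.5 introduces a list with "The following parameters on each ECG will be assessed by a cardiologist", and QRS is not named in it. But the same section has cardiologists review every ECG with its automated interval measurements, and the list ends with a general item on quantitative and qualitative variations.
- **That PYR alone is left unestimated because the endpoint omits it.** For QTc, the per-timepoint model compares each active treatment with placebo, PYR alone included.

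**Conclusion.** The point holds in a limited form. For PR and QRS the plan contains no placebo-adjusted estimate with a CI and no estimate of the PYR x PQP interaction, so this part of the secondary objective would be answered only by reading arm summaries side by side. That PYR and the combination are meant to cover the same list of parameters is an inference from the wording, though the natural one.

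The estimates would be informative but not sharp: under the assumed SD of 6 to 10 ms, roughly plus or minus 4 to 8 ms against placebo at N = 40, and somewhat wider with 37. The interaction would be less precise, at about 7 to 11 ms. These widths rest on the assumed SD and on balanced baselines. The finding itself rests on the text alone. It is a worthwhile, inexpensive improvement to an exploratory trial; it does not undermine the QTc analysis or the safety conclusions.

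**What to change.** In SAP 4.12, Per timepoint analysis, extend the outcome of the model sentence from QTc alone to QTc, PR and QRS. Keep the same factors, interaction, baseline covariate and two-sided 90% CIs. State that the added estimates support the secondary ECG objective, are descriptive and carry no multiplicity claim.

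Heart rate may be run through the same model. That would supply the mean time-matched difference to placebo which the 10 bpm rule already calls for, with its method of estimation stated.

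The cost is SAP wording and refitting a specified model to ECGs that the schedule already includes, with no added participants or visits. The programming is repetitive, since the model is fitted at each timepoint, and the tables grow by at least 63 intervals per parameter for Days 1 to 3. SAP 4.11.6 makes the adjudicated analyses subject to contract, so the added outcomes should be confirmed as within that scope. Protocol 10.1 requires SAP sign-off before database hard lock, and the change belongs before that point.

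If the sponsor intends PR and QRS to be descriptive only, saying so and narrowing the objective would remove the mismatch, but would leave the question unanswered.
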